## **Laboratory Evaluation**

Microbiologic studies for the secondary hypotheses will be conducted under the direction of [name], the Clinical Director of the Respiratory Virus Diagnostic

Laboratory at Baylor College of Medicine in Houston, Texas. The study involves collecting 2-8 nasal aspirates from each patient. Nasal aspirate samples will be tested to measure the levels of myeloperoxidase; we will also use ELISA tests to measure the levels of specific pro-inflammatory cytokines, including IL-8 and IL-6, and PCR, in order to screen for several major respiratory viral pathogens.

Nasal aspirate specimens will be collected at the first visit, the final visit, and during any episodic respiratory sick visits at clinic or at Children Memorial Hermann Hospital. These samples will all be frozen and stored until the completion of the trial. For the collection, the child will be placed supine, 2 ml of normal saline will be instilled into one nostril, and then an 8 or 10 French suction catheter (depending on the size of the patient) will be used to remove the mucus. This procedure will be performed once on each nostril. After the specimen collection from both nostrils, 2 ml of normal saline will be suctioned through the catheter to clear the tubing and to insure that a standard volume of aspirate is obtained. All specimens will be placed on ice in a bio-hazard bag and then collected by study personnel. After collection by study personnel, the specimen will be immediately diluted (1:1 solution) with viral transport medium (15% glycerol in Iscove's media). The final solution (aspirated specimen mixed with viral transport medium) will contain a maximum of 9 mls (with a range of 3-9 mls). After dilution, the specimens will be immediately refrigerated in the HRCC refrigerator at 37 degrees, until transportation to the freezers at the Department of Pathology at Baylor, where they will be stored at -80° C.

#### *Specimen Handling / Storage*

Nasal aspirate specimens will be transported by study personnel from the HRCC refrigerators to [name] laboratory. Once received, the dilution will be separated into 0.5 – 1 ml aliquots and snap frozen to -80° C. Samples will be thawed and centrifuged at 1,000g for 10 minutes at room temperature. This clarified nasopharyngeal lavage fluid supernatant will be used to measure the levels of myeloperoxidase, will undergo cytokine analysis, and will be screened for up to 5-6 major respiratory viruses. Remaining volumes will be stored for future studies,

including studies for additional biomarkers, such as Flu A, Flu B or other viruses. All specimens will be transported to [name] laboratory Monday – Thursday between 8am and 3pm and Friday between 8am and 1pm by involved research personnel walking to the laboratory. Specimens received Friday afternoon will be stored in clinic freezer until Monday morning. For during the weekend episodes, samples will be collected on Monday and properly marked with date and time of ER/Hospital visit and date and time of sample collection. Samples will be stored for one year after the completion of the study at [name] laboratory, and will be destroyed after the one-year period. Neither samples nor data will be shared outside of the University of Texas.

### *Labeling*

Specimens collected for this study must be easily distinguishable from other laboratory specimens stored in the Department of Pathology refrigerators and laboratory freezers. ID numbers will be pre-assigned and pre-printed on a label for each specimen. The date (mm/dd/yr) and time (hh:mm) of specimen collection must be written on the label. The ID number used for the case report form must match the ID number used on the specimen (eg, first patient 001 should be typed on the specimen labels and case report form). Specimens will also be labeled with date (mm/dd/yr) and time (hh:mm) of symptoms onset.

### *Laboratory Procedures*

The level of myeloperoxidase will be measured using reagent tests, and several cytokines that are markers of inflammation will be tested using ELISA tests. These tests are routinely performed in [name] laboratory and details of the primers and probes to be used are found in a 2005 article by Beckham et al. In addition, RT-PCR assays will be performed using TaqMan-based primers and probes to detect the presence of 5-6 major respiratory viruses, and the remaining volume of aspirate will be stored for future studies of additional biomarkers. Nasal aspirate samples will be collected for assay of up to 4 cytokines and chemokines. Samples will be tested according to the

manufacturer's instructions. Samples and serial dilutions of the cytokine standards will be incubated with anti-human cytokine-coated beads in a 96-well filtration plate.

## **Data Analysis Plan**

Patients will be randomized to one of two different branches by the REDCap data base randomization program. This will be a double-blind placebo controlled study. Standard frequentist and Bayesian analyses will be performed using an intent-to-treat approach. Total hospital days, total ER visits (counting one day for each ER visit), and unscheduled clinic visits (counting one day for each visit) for respiratory symptoms will be analyzed and related to treatment (Azithromycin vs Placebo), with logistic regression models and the treatment group as a covariate and random intercept to account for within patient correlation (due to multiple ED visits). To assess the probability of benefit, we will use Bayesian hierarchical models with interaction terms between treatment groups (Azithromycin vs Placebo) and predefined potential moderators. The groups will be stratified by palivizumab use and by tracheostomy on chronic mechanical ventilation. The conservative Bayesian approach of Dixon and Simon allows us to shrink the subgroup estimates to the overall mean treatment effect. For all Bayesian analyses, prior distributions for main effects will be neutral  $\sim N(0,1000)$ , and Uniform (0,1000) for SD parameters. Neutral and skeptical priors will be used for interaction terms. Point estimates of treatment effect and 95% credible intervals will be reported along with probability of treatment benefit.

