**The anti-inflammatory effect of prophylactic macrolides on children with chronic lung disease: a double blinded RCT**

**NCT02544984**

**Version date: 10/09/2015**

## **Research Aims**

### **Primary Aims:**

1. To determine if prophylactic use of azithromycin will reduce the total number of unscheduled face-to-face physician visit for respiratory related illness in a clinic, urgent care, emergency room or hospital setting during the 3-6 month study period, and subsequent 2 months follow-up.

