## **Study Outcomes**

1. In the treatment group, we expect a 20% total reduction in face to face encounters (defined as unscheduled sick visits, emergency room visits, and hospital admissions) for respiratory symptoms with the prophylactic use of azithromycin, as compared to the control group.
  - a. In the treatment group, we expect to have a 20% decrease in the number of unscheduled sick visits due to respiratory illness during the 3-6 month study period with the prophylactic use of azithromycin, as compared to the control group .
  - b. In the treatment group, we expect to have a 20% decrease in the number of Emergency Room visits due to respiratory illness during the 3-6 month study period with the prophylactic use of azithromycin, as compared to the control group.

- c. In the treatment group, we expect to have a 20% reduction in the number of hospital admissions due to respiratory illness during the 3-6 month study period with the prophylactic use of azithromycin, as compared to the control group.
2. In the treatment group, we expect a 10% total reduction (as compared to baseline) in the level of myeloperoxidase in the nasopharyngeal secretions collected during respiratory illnesses that require a face to face provider encounter, as compared to the control group.
3. In the treatment group, we expect a 10% total reduction in the level of pro-inflammatory cytokines in the nasopharyngeal secretions collected during respiratory illnesses that require a face to face provider encounter, as compared to the control group.
4. In the treatment group, we expect a 10% reduction from baseline in the level of airway obstruction as measured by a tremoFlo Airwave Oscillometry System during the 3-6 month study period, respiratory illness and at the conclusion of the intervention phase.
5. We expect no significant difference in adverse side effects between the treatment group receiving the macrolide and the control group receiving the placebo during the 4 month study.
6. We expect the intervention to be cost-effective from a healthcare system perspective.

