## **Sample size and power**

Based on data from our HRCC, we expect the control group to have 1.6 encounters per child-year (SD=1.66). Assuming a two-sided alpha = 0.05, a sample size of 90 (45/group) will have 80% power to detect a difference of 1 in the encounter rate between placebo and azithromycin groups (i.e., 1.6 vs 0.6 in encounter rate or 38% reduction). Power will be more limited for secondary outcomes but Bayesian analyses will provide an estimate of the probability of benefit in these outcomes.

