### **Interpretation and Potential Importance of Findings**

A substantial portion of our high risk chronically ill children have some form of chronic lung disease, including patients with tracheostomies, bronchopulmonary dysplasia, and chronic respiratory failure requiring mechanical ventilation. Most of the hospital admissions in this group of patients were related to respiratory infections in children less than 6 years of age (37% during the winter season for the previous 3 years). Despite vaccination rates of nearly 100% and 24/7 access to our clinic, viral respiratory illnesses continue to cause considerable morbidity and high healthcare costs. Innovative new prophylactic treatments are needed.

With this proposal, we will determine if the prophylactic use of azithromycin will 1) reduce the number of days when unscheduled medical treatment health care related encounters was given outside the home, 2) reduce the number of emergency room visits, hospitalizations and clinic visits due to respiratory illness, 3) reduce the level of myeloperoxidase and pro-inflammatory cytokines during viral illnesses requiring face to face physician interaction, 4) demonstrate a reduction in airway obstruction as measured by an oscillometer 5) have a similar safe profile compared to the placebo, and 6) demonstrate cost-effectiveness of macrolides use. Understanding the anti-inflammatory effects of azithromycin when used as a prophylactic drug will provide important insight into the prevention of more serious sequelae of respiratory infections. In particular, this proposal will contribute to understanding disease in children ages 6 months to 6 years with chronic lung disease, a population that has a higher rate of hospitalizations for respiratory symptoms.

3. Society AT. *Statement on the Care of the Child with Chronic Lung Disease of Infancy and Childhood* 2002. Accessed 8/19/14.

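### The analysis plan does not analyse the total number of visits that the primary aim names and the sample size rests on, and it names no deciding test.

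*Combined protocol and SAP*

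**What the plan says.** All places are in the combined protocol and SAP.

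- **Primary Aims.** There is one item: to "reduce the total number of unscheduled face-to-face physician visit for respiratory related illness in a clinic, urgent care, emergency room or hospital setting". The unit is a visit.
- **Study Outcomes, item 1.** A 20% reduction is expected in total encounters, defined as unscheduled sick visits, emergency room visits and hospital admissions. Items 1a to 1c then give each type its own 20% expectation; for 1c, "we expect to have a 20% reduction in the number of hospital admissions due to respiratory illness during the 3-6 month study period". An admission counts once, however long it lasts.
- **Sample size and power.** The control rate is 1.6 encounters per child-year with SD 1.66, and "Assuming a two-sided alpha = 0.05, a sample size of 90 (45/group) will have 80% power to detect a difference of 1" between the groups' encounter rates. This is a single comparison.
- **Data Analysis Plan.** The quantities related to treatment are "Total hospital days, total ER visits (counting one day for each ER visit), and unscheduled clinic visits (counting one day for each visit) for respiratory" complaints. Hospital use is now in days. The section names no primary variable, deciding test or multiplicity rule.
- **Interpretation and Potential Importance of Findings.** The trial is to determine, as item 1, whether azithromycin will "reduce the number of days when unscheduled medical treatment health care related encounters was given outside the home" and, as item 2, whether it will "reduce the number of emergency room visits, hospitalizations and clinic visits due to respiratory illness". Days and visit counts stand side by side.

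**The concern.** The Data Analysis Plan is the only text that says what will be analysed, and it does not contain the quantity that the trial is aimed at and sized on. The candidates can disagree. Clinic visits could fall while hospital days rise, or encounters could be unchanged while a few long admissions move the total of days. With visits, days and components all unranked, the result that decides the trial could be chosen after the data are seen. The 0.05 in the sample-size statement would then not describe the error rate of that choice.

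**Working it through.** **1. The plan's own figure.** Inputs from Sample size and power: difference 1, SD 1.66, two-sided 0.05, 80% power.

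n per group = 2 × SD² × (1.960 + 0.842)² / difference² = 2 × 2.756 × 7.849 / 1 = 43.3, so 44 per group or 88 in all, against the stated 90. At 45 per group the standard error is 1.66 × √(2/45) = 0.350 and the power is 81.5% (normal) or 80.7% (t). The statement reproduces, and it spends the whole 0.05 on one comparison of encounters.

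**2. Is that quantity analysed if the three are summed?** Let E be a child's encounters, with each admission, ER visit and clinic visit counted once. Let D be hospital days plus one day per ER or clinic visit. Then

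D − E = sum over admissions of (length of stay − 1).

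D equals E only if every admission lasts one day. As an illustration with assumed numbers, take a child with one ten-day admission, one ER visit and two clinic visits: E = 1 + 1 + 2 = 4 and D = 10 + 1 + 2 = 13. The documents give no mean or SD for D, so the stated power does not carry over to it.

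**3. Is it analysed if the three are kept separate?** No. Hospital days, ER visits and clinic visits would each be related to treatment, and none of them is the total.

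**4. Error rate on the separate reading.** Assume three tests, each at two-sided 0.05, with any one enough for a claim and no true effect.

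- Independent tests, either direction: 1 − 0.95³ = 0.143.
- Independent tests, favourable direction only: 1 − 0.975³ = 0.073.
- Correlated tests: three normal statistics with a common correlation. The documents give no correlation, so a range is shown.

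| Assumed correlation | At least one false positive, either direction | At least one false claim of benefit |
|---|---|---|
| 0 | 14.3% | 7.3% |
| 0.5 | 12.5% | 6.3% |
| 0.9 | 8.4% | 4.2% |
| 1 | 5.0% | 2.5% |
| Nominal, one test | 5.0% | 2.5% |

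**5. Error rate on the summed reading.** With one variable tested once at 0.05, there is no inflation from this source. The mismatch in step 2 remains.

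**The case against.** The strongest reply is that the plan means one summed variable. Counting one day for each ER or clinic visit does little unless those visits are to be added to hospital days. Item 1 of the Interpretation section describes just such a total of days. The documents also imply a hierarchy: there is one primary aim, the components are nested under the total in Study Outcomes, and the sample size covers a single rate. The trial is called a pilot, and it also commits to Bayesian estimates with a probability of benefit.

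Much of this stands, and it rules out a stronger reading. A reader might infer that the plan runs three parallel tests, so that a claim of benefit carries a false-positive rate of roughly 13% instead of 5%. The documents do not support that. They never say that the three are tested separately, or that one significant component meets the primary aim. A figure near 13% also needs an assumed correlation of about 0.4 to 0.5, and it counts errors in both directions, harm included. For false claims of benefit the rate is at most 7.3%, against 2.5%.

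The reply does not remove the mismatch. A sum of days is neither the visits of the primary aim nor the encounters of the sample size. Nor is the summed reading certain. The analysis text attaches the word total separately to hospital days and to ER visits, and speaks of models in the plural. It also adds a random intercept for repeated ED visits, which a single total per child would not need. The nesting in Study Outcomes suggests an order but sets no testing rule, and the stated secondary aims are adverse events and cost, not the components.

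**Conclusion.** The point holds as a mismatch between aim, sample size and analysis. Whichever way the Data Analysis Plan is read, following it as written does not test the total that the primary aim names, and no test is designated to decide the trial. This conclusion rests on the text alone.

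The size of any error inflation is conditional. It is zero if the quantities are summed and tested once. If they are tested separately and any one suffices, it is 8% to 14% for any two-sided false positive, and 4% to 7% for a false claim of benefit, at assumed correlations from 0.9 to 0. The rule that any one suffices is an assumption: the documents neither state it nor exclude it.

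**What to change.** In the Data Analysis Plan, state that the trial is decided by one contrast: azithromycin versus placebo on the total number of unscheduled respiratory encounters per child, tested at two-sided 0.05. Count each admission, ER visit or clinic visit once, in line with the Primary Aims, Study Outcomes and Sample size sections, and say where urgent-care visits, which the aim includes, are counted.

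Make total days of unscheduled care, hospital days, admissions, ER visits and clinic visits supportive, reported with estimates and 95% intervals. If claims on them are wanted, test them with Holm adjustment, and only after the total is significant. This keeps the days variable in the plan, whichever reading was meant. Reword Study Outcomes items 1a to 1c and Interpretation items 1 and 2 to match.

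The cost is a few sentences and no new data. The small downside is that a significant days or component result cannot be claimed as a positive trial when the total is not significant.

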## **Study Design and Methods**

### *Overview:*

This pilot randomized control trial (RCT) will enroll 92 children from 6 months to <6 years of age that have chronic lung disease (CLD) such as bronchopulmonary dysplasia during two seasons of respiratory illnesses defined as 1st October to 31st March of each year (2015-2016 Season and 2016-2017 Season). If the minimum number of patients (n=92) in Season 1 is achieved, we will then perform an interim analysis of the data. These children will all be patients who receive their primary medical care from either the High Risk Children Clinic or the similar High Risk Infant Clinic that cares for premature infants from discharge until age 2. Clinic records will be screened to determine eligibility. Patients that have parental consent will be given a baseline EKG, a nasal aspirate, an oscillometer reading (over 2 years of age only), and a three to six month supply of either the medication or the placebo at an initial study visit. Both medications will be taken once a day for three days a week: Monday, Wednesday and Friday. The azithromycin medication will be dosed at 5 mg/kg/day. Adjustments in dosage amount will be made with any new weights obtained during the trial period. Any child that is eligible to receive Palivizumab will be given this every 28-30 days in clinic as per usual care. Patients will be followed on a monthly basis and closely monitored for adverse reactions; this will occur by phone, in clinic during their regularly scheduled appointments, and/or during any necessary illness visits. Any children with adverse reactions will discontinue the medication, but will continue to be followed clinically. At any clinic visit in which a child presents with respiratory infections, including pneumonia,

upper respiratory illness, bronchiolitis, etc., he/she will have an additional nasal aspirate and/or tracheal aspirate if applicable and an oscillometer reading (only for children >2 years) performed. At the completion of the 3-6 months treatment phase, each child will have a final nasal aspirate and/or tracheal aspirate if applicable, and an oscillometer reading performed. Data will continue to be collected for the following 2 months (April 1st to May 31st), to monitor for respiratory illnesses and possible side effects.

*Study Population:*

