#### *Study Procedures:*

Patients will be randomized by the REDCap statistical program in a double blind manner. Parents will then be provided with a medication or placebo for the duration of the study. Patients would be recruited for this study on a rolling basis from October 1st to December 31st, and all patients completing the intervention part of the protocol on 31st March at the end of the season. Half of the patients will receive azithromycin at a

dose of 5 mg/kg to be given once a day on Monday, Wednesday, and Friday. The other half, the control group, will be provided with a placebo medication of similar taste, color, texture, and consistency, also to be taken once a day on Monday, Wednesday, and Friday. Both the study medication and the placebo will be dispensed from Corner Compounding Pharmacy, mixed with a fish-oil base to ensure a shelf life of more than six months, and flavored with citrus to improve palatability. Parents will be contacted biweekly, either in clinic or by phone, to monitor for any adverse reactions, including rash, nausea, vomiting, diarrhea, or abdominal cramping. If a significant adverse reaction occurs, the medication will be discontinued. If an allergic reaction (such as rash or shortness of breath) is noted, the blind will be broken by Research Coordinator [name], who is not involved with the project. This un-blinding will be done to note if it is an allergy to the medication.

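### The only frequentist model named, random-intercept logistic regression on days and visits, has no stated outcome or record unit, and no reading of it estimates the encounter rate that is the primary quantity

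*Combined protocol and SAP*

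**What the plan says.** **The quantity of interest.** The Primary Aim is to "reduce the total number of unscheduled face-to-face physician visit for respiratory related illness", over 3-6 months of treatment plus 2 further months. Study Outcomes, item 1, uses the same quantity: "we expect a 20% total reduction in face to face encounters (defined as unscheduled sick visits, emergency room visits, and hospital admissions". An admission is therefore one encounter, however long it lasts. Items 1a to 1c expect a 20% fall in each of the three components. Sample size and power works on the same scale: "we expect the control group to have 1.6 encounters per child-year (SD=1.66", with 45 children per group for a difference of 1 in that rate.

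**Follow-up.** Study Procedures says "Patients would be recruited for this study on a rolling basis" from October to December, with a common end of treatment on 31 March. Adding the 2 months, children are observed for about 5 to 8 months.

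**The analysis.** The Data Analysis Plan is the only analysis text. Its inputs are "Total hospital days, total ER visits (counting one day for each ER visit), and unscheduled clinic visits (counting one day for each visit", and these are related to treatment "with logistic regression models and the treatment group as a covariate and random intercept to account for within patient correlation". The reason it gives for the random intercept is repeated ED visits. The Bayesian sentences give priors, interactions and shrinkage, but no likelihood or link. No Poisson, negative binomial or other count model is named anywhere.

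**Days and visits.** The section on interpretation and importance of findings lists days of unscheduled care and numbers of visits and hospitalisations as two separate objectives. The Data Analysis Plan does not say which of them its model serves.

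**The concern.** Logistic regression needs a response coded yes or no for each record. The plan says neither what is coded nor whether a record is a child, a child-day or a visit. The primary comparison cannot be run until an analyst supplies both, and each choice changes what is estimated. The plan also counts every hospital day, whereas the aim and the outcome definition count admissions. A result on days of care would answer a different question from the one posed and powered. If the choice stays open, it could be made after outcomes have been seen.

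**Working it through.** **1. The plan's own sample size.** Inputs: difference 1, SD 1.66, two-sided alpha 0.05, power 80%. n = 2 × (1.960 + 0.842)² × 1.66² / 1² = 43.3, so 44 per group. The t-test version gives 44.2, rounded up to 45, with power 80.7% at 45. The stated 45 per group is reproduced, and it comes from a comparison of mean encounter rates. No logistic model lies behind it. (The 38% beside it fits 1.6 vs 1.0, not 1.6 vs 0.6. That is a separate issue.)

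**2. Reading (a): one record per child-day, components summed.** The random intercept and the counting in days favour this reading.

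*Is the logistic form at fault?* Let λ = 1.6/365 be the control rate per day. For a rate ratio of 0.375, the odds ratio for a day with an event is (e^(0.375λ) − 1)/(e^λ − 1) = 0.3745. For 0.8 it is 0.7996. In simulation with one-day encounters, 46 per arm and follow-up uniform over 5-8 months, the median odds ratio was 0.372. Power was 87%, against 86% for negative binomial. The form costs almost nothing.

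*Is the weighting at fault?* The documents give neither the admission share of encounters (a) nor the mean stay (L), so I assume a = 10-30% and L = 3-7 days. Then:

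- admission share of days = aL/(aL + 1 − a)
- visits cut by 20% only: encounter ratio a + 0.8(1 − a); day ratio (aL + 0.8(1 − a))/(aL + 1 − a)
- admissions cut by 20% only: encounter ratio 0.8a + 1 − a; day ratio (0.8aL + 1 − a)/(aL + 1 − a)
- both cut by 20%, stay unchanged: both ratios 0.80 for any a and L

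| a, L | Admission share of days | Visits only: encounters / days | Admissions only: encounters / days |
|---|---|---|---|
| 0.1, 3 | 0.25 | 0.82 / 0.85 | 0.98 / 0.95 |
| 0.2, 5 | 0.56 | 0.84 / 0.91 | 0.96 / 0.89 |
| 0.3, 7 | 0.75 | 0.86 / 0.95 | 0.94 / 0.85 |

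The day ratio understates an effect on visits and overstates an effect on admissions. A change in stay alone also separates the two. With 1.2 visits and 0.4 admissions per year (assumed), a stay shortened from 5 to 3.4 days gives an encounter ratio of 1.00 but a day ratio of (1.2 + 0.4 × 3.4)/(1.2 + 0.4 × 5) = 2.56/3.2 = 0.80.

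**3. Reading (b): a separate child-day model for each component.** ER and clinic visits count one day each, so those two models target visit rates. The hospital model still targets days, where item 1c of Study Outcomes has admissions. Nothing analyses the total in the Primary Aim.

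**4. Reading (c): any encounter, yes or no, one record per child.** With one record there is no within-patient correlation to estimate. In simulated data the log-likelihood was identical at random-intercept SDs of 0.01, 1, 2 and 4, while the odds ratio moved through 0.54, 0.47, 0.36 and 0.18. Repeat encounters are also lost. Assume negative binomial counts with k = (1.66² − 1.6)/1.6² = 0.451 and mean m = 1.6 × months/12. The share of control encounters after a child's first is 1 − [1 − (1 + km)^(−1/k)]/m:

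- 5 months (m = 0.667): 1 − 0.442/0.667 = 34%
- 8 months (m = 1.067): 1 − 0.581/1.067 = 45%

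**5. Would a count model rescue the 20% target?** With 45 per group and rate ratio 0.8, SE = √[(1/m₀ + 1/m₁ + 2k)/45] on the log scale. At 8 months this is √[(0.938 + 1.172 + 0.903)/45] = 0.259, and power is Φ(0.223/0.259 − 1.960) = 14%. At 5 months it is 11%. It would not.

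**The case against.** **Under the planned effect there is no divergence.** Items 1a to 1c expect the same 20% fall in every component, and with unchanged stay the day and encounter ratios are then both 0.80. This stands. But equal effects are a hypothesis, and the analysis should estimate encounters whether or not it is true.

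**A child-day logistic model is close to a rate model.** This also stands, and the number of day records carries the unequal follow-up. Coding only the first day of an admission would recover encounters, so negative binomial is not the only sound repair. The plan does not say this, however, and its wording counts every hospital day.

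**The components may not be summed.** The text does not state a sum. Reading (b) is open and is partly sound, but it leaves the total without a model.

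**Days may be what is meant.** Possibly. In that case the Primary Aim, Study Outcomes and the sample size describe the wrong quantity.

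**This is a pilot.** The Overview says so, but the sample size section still claims 80% power at two-sided 0.05.

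A reader might go further and infer that logistic regression here wastes power or inflates false positives. The evidence does not support that. With one-day encounters power matched negative binomial. With no effect and multi-day stays (the three a, L pairs above), rejection was 5.0%, 5.6% and 6.5% in 1,000 simulated trials each. The last is about two simulation standard errors above 5%, too little to claim inflation. Nor should the point rest on power lost by any/none coding, since that reading fits the random intercept least well.

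**Conclusion.** The concern holds as a mismatch between the stated method and the stated primary quantity. The Primary Aim, Study Outcomes and the sample size concern encounters. The only analysis text names a model with no outcome coding, record unit, follow-up handling or Bayesian likelihood, and none of its three readings estimates the encounter total. The claimed 80% power belongs to a different test.

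The size depends on where treatment acts. It is zero if visits and admissions fall equally and stay is unchanged. If only visits fall by 20%, encounters drop 14-18% and days 5-15%. If only admissions do, encounters drop 2-6% and days 5-15%. These ranges rest on the assumed admission share (10-30%) and mean stay (3-7 days), which the documents do not give. That the specification is missing rests on the text alone.

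A reader might also infer that an interim look is certain and that the choice of coding will be made on seen data. The Overview says "we will then perform an interim analysis of the data" only if 92 children are enrolled in Season 1, so this is a conditional risk. It is still reason to settle the specification before any outcome data are examined.

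**What to change.** - **Primary analysis.** Count unscheduled respiratory encounters per child, as defined in Study Outcomes, over the Primary Aim window. Use a regression for overdispersed counts, such as negative binomial, with log follow-up time as offset. Report the rate ratio with its 95% CI.
- **Bayesian model.** Use the same likelihood and link, so that the stated priors have a defined scale.
- **Covariates.** The plan says "The groups will be stratified by palivizumab use and by tracheostomy on chronic mechanical ventilation", between sentences on moderators and subgroup shrinkage. It may describe randomisation strata or subgroups. Say which, and adjust for both factors if they are randomisation strata.
- **Days.** Analyse days with unscheduled care as a separate outcome with its own stated model. Reconcile the Primary Aim, Study Outcomes, the Data Analysis Plan, the sample size and the list of objectives in the interpretation section. If the sponsor wants days as primary, the first two and the sample size must change to match.
- **Counting rule.** State how an ER visit that leads to admission is counted, before outcome data are seen and before any interim analysis.

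The cost is SAP wording and a different regression call, with no new data items. Days leave the primary endpoint and are reported alongside it. Power for a 20% reduction remains low.
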